4.3 Intervention

The intervention is the administration of a single dose of the ^{89}Zr -DFO-MSTP2109A tracer for imaging purposes. In Cohort 1A or 1B, after administration of the experimental tracer, the patient will undergo up to four PET scans during the 7 days post injection, whole body probe measurements and pharmacokinetics. In Cohort 2, patients will undergo injection of ^{89}Zr -DFO-MSTP2109A, and they will undergo one PET scan from top of skull to mid thigh (this may be adjusted based on known extent of disease) and no pharmacokinetics will be performed. The primary population will be those who are planning to enroll in the therapeutic trial using DSTP3086S (11-016), although for Cohort 1A, 1B and potentially Cohort 2 patients that meet the inclusion criteria may be enrolled even if not considered for DSTP3086S therapy. No clinical management decisions will be made based on ^{89}Zr -DFO- MSTP2109A imaging. Patients may not be re-imaged on this trial.

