9.5 Assessment for Toxicity

Safety Outcome Measures (CTCAE v4)

Infusion Reaction

Patients will be monitored during and after ⁸⁹Zr-DFO-MSTP2109A infusion for 90 minutes after the infusion. Patients who experience infusion-related symptoms should be managed as directed in Table 1.

The safety and tolerability of ⁸⁹Zr-DFO-MSTP2109A will be assessed using the following primary safety outcome measure:

- Incidence, nature, and severity of adverse events up to 1 week following antibody administration.
- Change in vital signs during administration

Table 1
 Management of Infusion-Related Symptoms

Infusion-Related Symptoms	Guidance
Grade 1	
 • Slow or hold infusion • Give supportive treatment • Upon symptom resolution, may resume infusion rate escalation at the investigator's discretion
Grade 2	
 • Slow or hold infusion • Give supportive treatment • Upon symptom resolution, may resume infusion-rate escalation at the investigator's discretion
Grade 3 or Grade 4	
 • Discontinue infusion • Give supportive treatment 
Patient may be imaged if sufficient tracer has been administered and the patient is stable, at the discretion of the administering investigator.

Given that this is a humanized antibody and the antibody will be administered only once under this protocol the likelihood of development of human anti human antibody is low. Patients enrolled, who are being treated with the ADC under protocol 11-016 will be monitored for the presence of anti-ADC antibodies as is currently stated in that study. Thus the presence, if any, of anti MSTP2109A, that would potentially interfere with ADC targeting will be evaluated in those patient on protocol 11-016. Baseline serum and 4-6 wk post infusion serum (serum separator or red top tube) will be collected and banked for future determination of HAHA response as requested by the FDA ([name] lab, storage approximately -70°C).

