10.0 EVALUATION DURING TREATMENT/INTERVENTION

Laboratory Safety Assessments

Blood testing:

Hematology and blood chemistry assessments (CBC, PSA, serum BUN, creatinine, AST, ALT, total bilirubin, alkaline phosphatase, albumin, blood glucose levels, and serum testosterone level) will be done at the time points described in Table 2. Additional blood tests may also be performed at the discretion of the investigator for the purposes of planning treatment administration, dose modification, or investigation and follow-up of adverse events. These additional tests will not be documented in the CRF.

Serum samples collected from baseline and 4-6 weeks after administration of DFO-MSTP2109A will be stored to assay for immune response to ⁸⁹Zr-DFO-MSTP2109A (assay to be developed). This assay may be done in house or shipped to Genentech for processing.

Physical examination:

A physical examination including, but not limited to, general appearance, skin, neck, eyes, ears,

MEMORIAL SLOAN-KETTERING CANCER CENTER IRB PROTOCOL

IRB#:12-178 A(3)

throat, lungs, heart, abdomen, lymph nodes, extremities, and nervous system will be performed. The physical examination will include examination of known and suspected sites of disease. Physical examination results, height and weight will be recorded at baseline .

Performance Status

Performance status will be assessed using the Karnofsky Performance Status scale (Appendix A).

Vital Signs

Blood pressure and heart rate will be obtained at the time points outlined in the flowchart.

Table 2
Schedule of Assessments

Cohort 1 (A and B):

	Screening ^a		Day 1	Day 2	Days 3-5	Days 6-8	4-6 wks post dose
	Within 4 weeks	Within 14 days					
Informed consent	X						
Demographics	X						
Medical history	X						
Concomitant medications	X						
Physical exam	X						
Performance status	X						
Vital signs^b	X		X	X	X	X	
Laboratory studies^c		X					X
Serum sample for banking		X					X
Radiographic studies^d	X						
IHC for STEAP^e	Prior to enrollment						
⁸⁹Zr-DFO-MSTP2109A tracer administration			X				

MEMORIAL SLOAN-KETTERING CANCER CENTER
 IRB PROTOCOL

IRB#:12-178 A(3)

Adverse events on day of imaging			X	X	X	X	
Serial whole-body scans (Cohort 1A and 1B)^f			X	X	X	X	
Serial whole-body probe^g			X	X	X	X	
Serial blood samples^h(Cohort 1A and 1B)			X	X	X	X	

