^a Screening evaluation should be performed following informed consent and within 4 weeks before study entry, except when noted otherwise. Evaluations performed as standard of care before informed consent but within the 4-week window need not be repeated.

^b Vital signs will be monitored prior to infusion and every 30 minutes for at least 2 h or later if the patient is still in the department for imaging.

^c Within 14 days laboratory studies include CBC, PSA, serum BUN, creatinine, AST, ALT, total bilirubin, alkaline phosphatase, albumin, blood glucose levels, and serum testosterone level. All laboratory studies are to be performed up to 2 weeks before study entry (serum testosterone level may be up to 4 weeks before study entry). At Days 6 to 8 CBC and comprehensive labs will be obtained.

^d Radiographic evaluations include bone scintigraphy, CT of chest, abdomen and pelvis (MRI is acceptable if CT is clinically contraindicated), and modified MRI of the pelvis, if clinically indicated. All radiographic studies are to be performed within 4 weeks before, or up to 2 weeks after study entry, provided the patient has not received treatment.

^e sample sent out to Genentech

^f Following injection with the ⁸⁹Zr-DFO-MSTP2109A tracer, the patients enrolled in the study (Patients Cohort 1 A and or 1B) will have serial whole-body PET-CT scans (WBS) performed to determine the biodistribution of the tracer. PET scans will be acquired: 1–4 hours following injection of the tracer, ~24 h \pm 8 h post-injection, ~48–96 hours post injection, and ~120–168 hours post injection. Slight variations in times due to scheduling or technical difficulties will not be considered violations

^g Whole body counts (WBC) using a probe will be performed during the imaging in the first 12 patients and the exact time recorded:

- Within 0.1 to four hours following injection of tracer on Day 1 (prior to voiding) and post voiding
- 24 \pm 8 hours post-injection (Day 2)
- ~48–96 hours post-injection (once during Days 3–5)
- ~120–168 hours post injection (once during Days 6–8)

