^h For the first 12 patients enrolled, serial blood samples will be obtained for biodistribution, metabolite analysis of the ⁸⁹Zr-DFO-MSTP2109A compound will be performed on selected samples. Samples will be obtained just prior to injection of the ⁸⁹Zr-DFO-MSTP2109A tracer, and at 5 \pm 2 minutes, 15 \pm 5, 30 \pm 9, 60 \pm 19 minutes, and 120 – 240 minutes after the injection of the tracer on 24 \pm 8, and at the time of each subsequent day of imaging , ~48-96, ~120-168, slight variations in times due to scheduling or technical difficulties will not be considered violations.

Cohort 2:

	Screening ^a		Day 1	Day TBD	Follow up	
	Within 4 weeks	Within 14 days			~1 weeks post dose (Day 6-8)	4-6 weeks post dose
Informed consent	X					
Demographics	X					
Medical history	X					
Concomitant medications	X					
Physical exam	X					
Performance status	X					
Vital signs^b	X		X	X		
Laboratory studies^c		X		X		
Serum sample for banking		X				X
Radiographic studies^d	X					

⁸⁹ Zr-DFO-MSTP2109A tracer administration		X				
Adverse events		X	X	X		
Phone assessment^e				X	X	

- a Screening evaluation should be performed following informed consent and within 4 weeks before study entry, except when noted otherwise. Evaluations performed as standard of care before informed consent but within the 4-week window need not be repeated.
- b Vital signs will be monitored prior to infusion and every 30 minutes for at least 2 h or later if the patient is still in the department for imaging.
- c Laboratory studies include CBC, PSA, serum BUN, creatinine, AST, ALT, total bilirubin, alkaline phosphatase, albumin, blood glucose levels, and serum testosterone level. All laboratory studies are to be performed up to 2 weeks before study entry (serum testosterone level may be up to 4 weeks before study entry). Second set of laboratory on TBD will consist of CBC and comprehensive. At TBD CBC and comprehensive will be repeated.
- d Radiographic evaluations include bone scintigraphy, CT of chest, abdomen and pelvis (MRI is acceptable if CT is clinically contraindicated), and modified MRI of the pelvis, if clinically indicated. All radiographic studies are to be performed within 4 weeks before, or up to 2 weeks after study entry, provided the patient has not received treatment.
- e A phone call will be used to assess for changes in concomitant medications and any adverse events after all scans have been completed if the scanning time is less than 6-8 days.

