16.3 Data and Safety Monitoring

The data and safety monitoring (DSM) plans at MSKCC were approved by the National Cancer Institute in September 2001. The plans address the policies set forth by the NCI in the document entitled *Policy of the National Cancer Institute for Data and Safety Monitoring of Clinical Trials*, which can be found at <http://cancertrials.nci.nih.gov/clinicaltrials>. The DSM plans at MSKCC were established and are monitored by the Office of Clinical Research. The MSKCC DSM plans can be found on the MSKCC Intranet at: <http://mskweb5.mskcc.org/intranet/html/70775.cfm>.

There are several different mechanisms by which clinical trials are monitored for data, safety, and quality. There are institutional processes in place for quality assurance (e.g., protocol monitoring, compliance and data verification audits, therapeutic response, and staff education on clinical research quality assurance) and departmental procedures for quality control, and there are two institutional committees that are responsible for monitoring the activities of our clinical trials programs. The committees: *Data and Safety Monitoring Committee (DSMC)* for Phase I and II clinical trials, and the *Data and Safety Monitoring Board (DSMB)* for Phase III clinical trials, report to the MSKCC Research Council and Institutional Review Board.

During the protocol development and review process, each protocol will be assessed for its level of risk and degree of monitoring required. Every type of protocol (e.g., NIH sponsored, in-house sponsored, industrial sponsored, NCI cooperative group, etc.) will be addressed, and the monitoring procedures will be established at the time of protocol activation.

For this protocol, we will use the following patient safety monitoring plan and monitoring for adverse events, in terms of the test performed and their timing relative to injection (see Table 1 and 2). Patient will be observed closely during infusion and serial vital signs will be monitored every half hour for at least 2 h or later if the patient remains in the department. Patients will be queried for adverse events up to 6-8 days after infusion.

Safety reviews will be performed by the MSKCC-DSMC with yearly review by the IRB.

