17.4 SAE Recording and Grading

17.3.1 Recording

The investigator must assess each event to determine if it meets the criteria for classification as a serious adverse event (SAE) or serious adverse drug reaction (ADR). An SAE/ADR as defined in the Code of Federal Regulations (21CFR312.32) is any event that:

- Results in death
- Is life-threatening
- Results in inpatient hospitalization or prolongs an existing hospitalization
- Results in persistent or significant disability/incapacity
- Results in congenital anomaly/birth defect
- Is medically significant in the opinion of the investigator

All SAEs that occur any time a patient is on study (i.e., as soon as the informed consent has been signed) or within 30 days of the ⁸⁹Zr-DFO-MSTP2109A scan must be reported, regardless of the suspected relationship to ⁸⁹Zr-DFO-MSTP2109A. Any SAE occurring more than 30 days after the ⁸⁹Zr-DFO-MSTP2109A scan must be reported if a causal relationship to ⁸⁹Zr-DFO-MSTP2109A is suspected.

Because the subjects enrolled in this clinical investigation will be exclusively patients with advanced prostate cancer, these patients will typically have received extensive medical care before and at the time of enrollment in the study. Such medical care includes extensive diagnostic radiological studies, such as x-rays, CT scans, and nuclear medicine studies (e.g., bone scans) and, in at least some cases, external beam radiation therapy, brachytherapy, or both. The additional radiation doses associated with the ⁸⁹Zr-

DFO-MSTP2109A study will typically represent a small increment in their “lifetime” exposures, given the number of clinical studies (CT, bone scan, FDG scan) and that many of these patients will have had primary radiation to their prostate or external beam radiation to bone.

When accounting for many tests per year, the radiation doses (on the order of 10 rem) lie well within the “low-dose” range—well below the threshold doses (typically on the order of 100 rem or greater) for any known deterministic effects. A detailed description of the expected dosimetry from the ^{89}Zr -DFO-MSTP2109A is included (Table 3). The dose of ^{89}Zr -DFO-MSTP2109A per administration (~5mCi) gives the lowest amount that would be consistent with the research goal, namely, biodistribution, metabolism, and pharmacokinetics of the compound.

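### Cohort 1 has no scheduled adverse-event query after the last imaging visit, so most or all of the 30-day SAE window is unqueried and the 1-week outcome can fall up to 48 h short

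*Combined protocol and SAP*

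**What the plan says.** Five places in the protocol bear on when Cohort 1 patients are asked about adverse events.

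- **Outcome (section 9.5).** The primary safety measure is "Incidence, nature, and severity of adverse events up to 1 week following antibody administration".
- **Schedule (section 10.0, Table 2, Cohort 1).** The row is titled "Adverse events on day of imaging". It is marked on Day 1, Day 2, Days 3-5 and Days 6-8, the same columns as the scans, probe counts and blood samples. The 4-6 week column has no adverse-event or concomitant-medication mark, although serum for banking is marked there and section 9.5 also calls for that sample. The footnotes place the last visit at "120–168 hours post injection (once during Days 6–8").
- **Monitoring plan (section 16.3).** "Patients will be queried for adverse events up to 6-8 days after infusion". The same paragraph defines the plan "in terms of the test performed and their timing relative to injection (see Table 1 and 2"), so its timing refers back to the schedule.
- **SAE recording (section 17.3.1).** The reporting duty covers "All SAEs that occur any time a patient is on study (i.e., as soon as the informed consent has been signed) or within 30 days", with those days counted from the scan, and it applies whatever the suspected relationship. The text does not say which of the Cohort 1 scans is meant.
- **Cohort 2 (Table 2, footnote e).** A phone call asks about changes in medication and "any adverse events after all scans have been completed if the scanning time is less than 6-8 days". Cohort 1 has no such row or footnote.

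**The concern.** A site that follows the Cohort 1 schedule exactly asks about adverse events for the last time at the final imaging visit. Two windows extend beyond that point: the 1-week primary safety outcome, by a little, and the 30-day SAE reporting period, by a lot. A duty to report covers only what the investigator learns of. Without a scheduled question, an SAE treated elsewhere in weeks 2 to 5 comes to light only if the patient volunteers it or another team passes it on.

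This matters because section 3.2.2 says that the intact antibody has not been given to humans, and section 4.2 says that the tracer has not been evaluated in patients. Under section 14.2, Cohort 1A must be free of severe toxicity attributable to the 10 mg dose before Cohort 1B opens, and a grade 3 or 4 event in any cohort goes to the monitoring committee and the IRB before accrual continues.

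**Working it through.** The plan states no figure to reproduce. The check compares visit windows, with time counted from injection on Day 1.

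**Inputs.** Last Cohort 1 imaging visit: 120-168 h (Table 2 footnotes; section 9.3). Third imaging visit: 48-96 h (same places). Primary safety window: 1 week = 7 × 24 = 168 h (section 9.5). Questioning promised: up to 6-8 days after infusion (section 16.3). SAE window: 30 days after the scan (section 17.3.1). Late blood draw: 4-6 weeks = day 28-42 (section 9.5 and Table 2).

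**1. The 1-week outcome, planned schedule.**
- Last query: 120/24 = 5 days to 168/24 = 7 days after injection.
- Shortfall: 168 − 168 = 0 h to 168 − 120 = 48 h.
- Against the lower limit in section 16.3 (6 days after infusion): at most 6 − 5 = 1 day.

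**2. The 1-week outcome, Days 6-8 visit missed.**
- Last query at 48-96 h; shortfall 168 − 96 = 72 h to 168 − 48 = 120 h, that is, 3 to 5 days.
- Section 4.3 says "the patient will undergo up to four PET scans during the 7 days post injection", which does not guarantee the fourth scan. Section 9.3 and Table 2 footnote f do schedule all four, so this is a missed-visit case and not the plan.

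**3. The 30-day SAE window.**
- Clock from the last scan (day 5-7): the window closes at 5 + 30 = day 35 to 7 + 30 = day 37. The last query is on the day the window opens, so all 30 days follow it.
- Clock from the Day 1 scan: the window closes at about day 30. Days after the last query: 30 − 7 = 23 to 30 − 5 = 25.

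**4. Would a query at the 4-6 week blood draw be enough?**
- Clock from the last scan: a draw on day 28 leaves 35 − 28 = 7 to 37 − 28 = 9 days of the window unqueried. A draw on or after day 37 covers it in every case.
- A query at the draw therefore needs a call behind it when the draw is early.

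**The case against.** The strongest reply is that the 1-week outcome is essentially met as planned. Cohort 1 has an adverse-event mark at Days 6-8, and the Cohort 2 table labels those same days as about one week after dose. Vital signs are marked then, and footnote c adds blood tests, so the contact does not rest on the scan alone. Section 16.3 separately commits to questioning patients through about that time. This largely stands. It limits the planned shortfall to 0-48 h, though section 16.3 takes its timing from the table and so does not supply a separate contact.

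A second reply is that section 14.2 restricts evaluation to short-term toxicity because new therapy is likely within 2 weeks. That explains the 1-week outcome. It does not remove the 30-day reporting duty, which applies regardless of cause.

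Three stronger readings are tempting, and the documents support none of them:

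- A reader might infer that Cohort 1 has weaker ascertainment than Cohort 2. Within the first week it has four in-person checks, whereas Cohort 2 has one scan visit after injection and a conditional call.
- A reader might infer that primary incidence is understated for want of a late query. Events after 1 week lie outside that outcome, so they cannot lower it.
- A reader might infer that the cohorts cannot be pooled on one window. Questioning is planned through Days 6-8 in both.

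Nor is there a case for editing the Cohort 2 table. It is broken in the text available here, but read with its columns realigned it appears to mark a phone assessment at 4-6 weeks already.

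**Conclusion.** The point holds in two parts of unequal weight. The main one is the SAE window: Cohort 1 carries a 30-day reporting duty but has no scheduled query after Days 6-8. That leaves 30 of 30 days uncovered if the clock starts at the last scan and 23-25 if it starts at the Day 1 scan. The range exists because section 17.3.1 does not say which scan counts. The lesser part is the 1-week outcome, where the last query can fall up to 48 h short on the planned schedule. The shortfall is 3 to 5 days only if the Days 6-8 visit is missed, and Cohort 1 has no named back-up for that.

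Uncovered here means after the last scheduled question. Patients treated under protocol 11-016 may be seen there, and events between visits can be elicited at the next one. The finding is a gap in the schedule, not evidence that events will be missed. It is worth correcting because the patient already returns within the relevant period.

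**What to change.** 1. Add an adverse-event, SAE and concomitant-medication query to the existing Cohort 1 contact at 4-6 weeks, with a brief call at day 30 after the last scan if that contact falls earlier.
2. Extend the phone call in Cohort 2 footnote e to Cohort 1 patients whose last visit is missed or falls before the end of the 1-week window.
3. State in section 17.3.1 which scan starts the 30-day window, and reconcile Table 2 with sections 9.5, 16.3 and 17.3.1 so that each gives the same period for adverse events and for SAEs.

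The cost is small but reaches more than a few patients, since any last scan before 168 h triggers the 1-week call. With up to 6 patients in each of Cohorts 1A and 1B and at most two calls each, the ceiling is 12 × 2 = 24 short calls, plus a few case report form lines at a visit already planned. The analytic cost is that some late events will be due to new therapy. They should be flagged with the start date of that therapy and reported separately from the 1-week outcome.

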11.0 TOXICITIES/SIDE EFFECTS

Risks

⁸⁹Zr-DFO-MSTP2109A PET/CT Scans

As part of this scan there is radiation delivered from the ⁸⁹Zr and from the low dose CT scan that are performed as part of the CT for attenuation correction and co-registration. Although any exposure to ionizing radiation has the potential to cause some harm to tissue, the radiation exposures in this study are comparable to the low-level exposures associated with common diagnostic procedures such as CT scanning. There remains a low theoretical risk of developing a cancer at some point later in life as a result of the radiation exposure received in this study. This risk is particularly low for adults given the fact that the radiation from the scans will be over several weeks. Participants should not father a baby while on this study. Acceptable birth control methods include abstinence, double barrier method, surgically sterilized patient or partner. This risk is much smaller than the clinical risks posed by the patient's current cancer.

DFO-MSTP2109A

Potential risks associated with DFO-MSTP2109A are similar to those of other humanized antibody and include allergic reactions, characterized by fever, chills, and sometimes rashes or hives. Less likely shortness of breath can occur. Rare allergic reactions can present as shock or death or swelling of the throat. Such reactions are usually addressed by stopping the administration of the drug, administering steroids, acetaminophen and/or diphenhydramine, and restarting the drug at a slower rate if the reaction is not severe.

There is a very small risk of infection. This could cause itching or redness at the area on the patient's arm where the IV was placed.

Radiation Dosimetry

Normal-organ radiation absorbed doses and the effective dose for ^{89}Zr -DFO-MSTP2109A in human were estimated based on measured time-activity data in mice. The time-activity data (percent of the injected dose per gram (%ID/gm) versus time (t) post-administration) for each organ were fit to an exponential functions and the resulting function were analytically integrated (incorporating the radioactive decay of ^{89}Zr) to yield the residence time (cumulated activity) of ^{89}Zr in each organ. The mouse organ ^{89}Zr residence times were converted to ^{89}Zr residence times in human organs (for the 70-kg Standard Man anatomic model) by adjusting for the difference in fractional organ masses between mice and humans. The resulting human residence times were then entered into the OLINDA/EXM radionuclide dosimetry program, which implements the MIRD (Medical Internal Radionuclide Dosimetry) algorithm, to yield the normal-organ radiation absorbed doses (in rad) and effective dose (in rem) for ^{89}Zr -DFO-MSTP2109A in man. Assuming a 5-mCi administered activity of ^{89}Zr -DFO-MSTP2109A and a low-dose (80 mA) and three very-low-dose (10-mA) CT scans are to be performed, with approximate CT effective doses of 0.90 rem and 0.11 rem the radiation dosimetry is tabulated below.

Table 3. ^{89}Zr -DFO-MSTP2109A Absorbed Doses in 70-kg Standard Man per MIRD (OLINDA) Formalism Based on Biodistribution Data in Mice¹

^{89}Zr -DFO-MSTP2109A AP Antibody Radiation Doses in the 70-kg Standard Man

^{89}Zr Administered Activity:	5	mCi
# of 80-mA CT scans:	1	
Organ dose per 80-mA CT scan:	0.90	rem
# of 10-mA CT scans:	3	
Organ dose per 10-mA CT scan:	0.10	rem
Total CT organ dose:	1.20	rem

	Absorbed Doses		
	^{89}Zr -DFO-MSTP2	P2109A	
		rad/5	rad/mCi
Adrenals	1.56	7.80	9.00
Brain	0.68	3.42	4.62
Gallbladder Wall	1.32	6.60	7.80
LLI Wall	1.52	7.60	8.80
Small Intestine	1.25	6.25	7.45
Stomach Wall	1.39	6.95	8.15
ULI Wall	1.34	6.70	7.90
Heart Wall	1.50	7.50	8.70
Kidneys	2.33	11.7	12.9
Liver	1.81	9.05	10.25
Lungs	2.82	14.10	15.30

MEMORIAL SLOAN-KETTERING CANCER CENTER
IRB PROTOCOL

IRB#:12-178 A(3)

Muscle	1.21	6.05	7.25
Pancreas	1.42	7.10	8.30
Red Marrow	3.26	16.3	17.5
Osteogenic Cells	4.59	23.0	24.2
Skin	0.71	3.55	4.75
Spleen	1.98	9.90	11.10
Testes	0.82	4.09	5.29
Thymus	1.11	5.55	6.75
Thyroid	1.03	5.15	6.35
Urinary Bladder Wall	1.04	5.20	6.40
Total Body	1.31	6.55	7.75
Effective Dose Equivalent	1.87	9.35	10.55
Effective Dose	1.68	8.40	9.60

¹mouse data obtained with ⁸⁹Zr-DFO-MSTP2109A, conjugate generated at MSKCC. .

